## 6.2 Subject Disposition and Data Sets Analyzed

Subject disposition will be listed and summarized by treatment group and overall and will include the number and percentage of subjects:

- Screened;
- Randomized;
- Not randomized;
- Randomized and not treated;
- Treated;
- Included in each study population (Safety, ITT, mITT, DXA Substudy);
- Completed all study visits;
- Completed all study visits on study drug;
- Randomized but discontinue study drug and discontinue from all study visits and procedures;

- Randomized but discontinue study drug but continue with all study visits and procedures; and
- Randomized but discontinue from the study and returned for the Week 56 weight measurement.

For subjects who are not randomized, randomized subjects who discontinue study drug but continue in the study, and randomized subjects who discontinue study drug and study participation, a summary regarding reason of discontinuation will also be provided.

A summary of patient enrollment by site will also be provided by treatment group and overall for the Safety population.

### **6.3 Protocol Deviations**

A protocol deviation is any change, divergence, or departure from the study design or procedures defined in the protocol. Protocol deviations for the study include, but are not limited to, the following:

- Failure to meet inclusion/ exclusion criteria;
- Non-compliance of protocol guidelines;
- Inability to adequately complete study assessments per protocol, etc.

Failure to comply with Good Clinical Practice (GCP) guidelines will also result in a protocol deviation. The Sponsor will determine if a protocol deviation will result in withdrawal of a subject.

All protocol deviations and deviation categories will be listed and summarized for the Safety population.

### **6.4 Demographics and Other Baseline Characteristics**

Demographic and baseline characteristics will be listed and summarized by treatment group and overall for randomized, Safety and DXA substudy populations. Standard descriptive statistics will be presented for the continuous variables of:

- Age at screening (years)
- weight (kg)
- height (cm)
- body mass index (kg/m^2)
- Waist Circumference (cm)
- Fasting insulin
- Whole Body Insulin Sensitivity Index (Matsuda)
- Triglycerides
- HDL-C

- Systolic Blood Pressure (mmHg)
- Diastolic Blood Pressure (mmHg)

The total counts and percentages of subjects will be presented for the categorical variables of:

- Age at screening (12-14 years, 15-16 years)
- Gender
- Race
- Ethnicity
- BMI categories  $\geq 95^{\text{th}}$  to  $< 99^{\text{th}}$ , and  $\geq 99^{\text{th}}$  percentile)

No formal tests of statistical significance will be performed on the demographic and baseline data.

Other baseline measurements, such as vital signs, ECG, will be summarized by treatment group with the post-baseline measurements.

#### **6.4.1 Medical History**

Medical history will be coded using the Medical Dictionary for Regulatory Activities (MedDRA) Version 21.3 (or a later version if updated during the study). All medical history will be listed, and the number and percentage of subjects with any medical history will be summarized for Safety population by system organ class (SOC) and preferred term (PT) for each treatment group and overall.

#### **6.4.2 Prior and Concomitant Medications**

Medications received prior to or concomitantly with study drug treatment will be coded by [REDACTED] using the WHO Drug Global Dictionary, Version September 2018 (or a later version if updated during the study), Anatomical Therapeutic Chemical (ATC) Classification codes.

Medications, other than study medication, taken within 30 days prior to screening will be considered as prior medications; while those taken during the study will be considered as concomitant medications.

If a medication cannot be classified as "prior" or "concomitant" after applying imputation rules for missing/incomplete dates, it will be classified as concomitant.

Prior medications and concomitant medications will be listed and summarized together for Safety population.

The number and percentage of subjects using each medication will be displayed together with the number and percentage of subjects using at least one medication within each therapeutic class (ATC-Level 2), chemical subgroup (ATC-Level 4), and preferred term.

## 6.5 Measurements of Treatment Compliance

Percentage compliance is calculated as:

$100 * \text{actual capsules taken} / \text{expected capsules taken}$

Where actual capsules taken is defined as (total number of capsules dispensed – total number of capsules returned) and expected taken is defined as the number of capsules prescribed per day times the number of days taken for study treatment.

Percentage compliance will be summarized descriptively by treatment group for the Safety population.

The number and percentage of compliant subjects will be presented for the Safety population, where compliant is defined as percentage compliance between 80.0% and 120.0% inclusive. The following percentage compliance categories will also be presented:

- <80.0%
- 80% to 120%
- >120.0%

## 6.6 Efficacy

### 6.6.1 Primary Efficacy Analysis

The primary endpoint for this study is the mean % change in BMI from baseline to end of study (Week 56).

For subjects who discontinue treatment prior to trial completion, every attempt will be made to have them continue with clinic visits and study assessments. Particular attention will be given to collecting Week 56 assessments of weight and height, regardless of when subjects discontinued treatment. These retrieved dropouts will be used to impute missing data using multiple imputation method for the primary analysis for subjects who discontinue the study prematurely and are missing follow-up observations. This is based on the assumption that the group that best reflects what happened to the non-retrieved dropouts at week 56, are the retrieved dropouts. For patients who terminate the treatment early but decide to stay in the study and have all the data after being off treatment, those data will be used to impute the missing data off-treatment. For any patient who terminates the treatment and study prematurely and permanently, if the patient has the final measurement at Week 56, the measurement will be used for analyses at Week 56. The missing data between the last available measurement and Week 56 will be imputed by interpolation for analyses.

If there are no sufficient retrieved dropouts, the washout imputation method will be applied. This imputation method will only impute the time point at Week 56 for the

active treatment arms using multiple imputation regression with randomization strata and baseline BMI as the predictors. This approach ignores any post-baseline changes in the BMI values when predicting missing Week 56 values and will impute all patients similar to an average placebo patient. For patients in placebo arm, missing data at any time point will be imputed assuming MAR mechanism. The variables used as explanatory variables for imputation include Randomization strata and baseline BMI.

After such imputation, comparisons in the primary endpoint of change from the baseline BMI between treatment groups be assessed for the ITT population using a mixed effects model with repeated measures (MMRM) with factors of treatment, visit, treatment by visit interaction, baseline BMI value, age stratification, and gender stratification. Appropriate contrast will be applied for treatment comparisons at Week 56. The pairwise comparisons of interest are top-dose vs. placebo, and mid-dose vs. placebo, and top-dose vs. mid-dose. The primary null hypothesis will be that there is no treatment difference between any VI-0521 treatment groups and the placebo in the percent change from baseline to Week 56 in BMI. An appropriate contrast will be used for the comparisons at Week 56. The family-wise type 1 error for the comparisons will be controlled by Fisher's protected least significant difference (LSD) method at the 0.05 significance level: placebo, mid-dose, and top-dose will be first compared for overall difference in the percent change from baseline in BMI. Once the overall difference is significant at the 0.05 significance level, the above 3 pairwise comparisons will be conducted using Fisher's LSD method at the 0.05 significance levels. The order for comparisons of interest is top-dose vs. placebo, mid-dose vs. placebo, and top-dose vs. mid-dose. Due to the fact that only three treatments are compared, the above procedure strongly controls the family-wise type 1 error.

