All subjects will return at approximately 4-week intervals for study assessments. All female subjects will undergo a pregnancy test at each visit. Subjects who discontinue study drug during the study will be encouraged to remain on study (off study drug) for continued follow-up by attending all remaining visits and have all study-related procedures performed, and to return at the 56-week time point for measurements and evaluations. For those who choose to completely withdraw from the study at any point, the end of study (Week 56) procedures should be completed.

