**Figure 1. Schematic Diagram of Study Design**

## 2.3 Sample Size and Power

In previous studies in adults, VI-0521 mid-dose (PHEN/TPM 7.5 mg/46 mg) resulted in a placebo-subtracted BMI reduction of 2.4 units with a standard error approximately 0.16 units and a within treatment standard deviation of 2.9. A very conservative estimate of the treatment difference between the mid-dose and placebo would be 2 units of BMI which represents more than 2 standard errors below what was observed before. If we enroll 200 subjects (50 placebo, 50 mid-dose, and 100 top-dose), we will have at least 90% power to detect a statistically significant difference between the top-dose (PHEN/TPM 15 mg/92 mg) and the placebo because we could assume that the top-dose will have a higher effect size than the mid-dose. This calculation assumes that there will be an approximately 30% dropout rate. This sample size will also provide approximately 80% power to detect a statistically significant difference between the mid-dose and placebo.

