## 6. Statistical Methods

### 6.1 General Principles

All data processing, summarization and analyses will be performed using SAS Environment / Version 9.3 (or later) of the SAS® statistical software package.

The following principles will be applied to all TFLs unless otherwise stated:

Principle	Value
Significant tests	Two-sided and use a 5% significance level.
Treatment group labels and order presented	Placebo VI-0521 Mid VI-0521 Top
Tables	Data in summary tables presented by treatment group, assessment and visit (where applicable).
Listings	All data collected presented by treatment group, site, subject, and visit (where applicable), unless otherwise specified.
Descriptive summary statistics for continuous variables	Number of observations (N), mean, standard deviation (SD), minimum, median and maximum.
Descriptive summary statistics for categorical variables	Frequency counts and percentages [n (%)].
Denominator for percentages	Number of subjects in the pertinent analysis population, unless stated otherwise in table shells.
Include "Missing" as category	Demographics and Other Baseline Characteristics only
Display for 0 percentages	Blank
Display to one more decimal place than collected value	Mean Median Minimum Maximum
Display to two more decimal places than collected value	Standard Deviation Confidence Interval
Limit of precision for displays	3 decimal places
Date Format	DDMMYYYY

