Secondary efficacy endpoints that are continuous variables (change from baseline in waist circumference, fasting insulin, whole body insulin sensitivity index (Matsuda), triglycerides, HDL-C, and systolic and diastolic blood pressure) will be analyzed by a similar MMRM model as for the primary endpoint where the baseline BMI value will be replaced by the baseline value of the corresponding endpoint as a covariate.

The above analyses will be conducted for both the ITT and mITT populations.

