### 6.6.3 Sensitivity Analysis

The MMRM method used for the analysis will be applied to the mITT population with the observed data without imputation. The following sensitivity analyses will also be considered to explore the impact of missing data on the conclusion of the primary analysis.

The first sensitivity analysis is using a multiple imputation method based on the monotonic missing pattern under the assumption of MAR. The intermittent missing data will be imputed using multiple imputation MCMC procedure.

The second sensitivity analysis is also using multiple imputation, however, under the assumption of MNAR to explore the validity of MAR using pattern-mixture model:

1) For subjects who discontinue study participation prior to Week 56 and do not have follow-up visit, the missing data will be imputed using the observed data from the subjects in the same arm who discontinue the study treatment but have the primary endpoint measurement in the follow up visit using a regression method. The

intermittent missing data will be imputed using multiple imputation MCMC procedure. An ANCOVA model using a similar mixed procedure (without the repeated measures) as the primary analysis will be applied to these multiple-imputed % change in BMI at Week 56 with treatment, baseline BMI value as a covariate, and age and gender as stratification factors. The results of ANCOVA analysis on the multiple imputed datasets will be combined and summarized.

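### The primary MMRM has no covariate-by-visit terms, so precision at Week 56 may be lost if baseline BMI, age and gender effects build up over follow-up

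*SAP*

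**What the plan says.** SAP 6.6.1 fits the primary MMRM "with factors of treatment, visit, treatment by visit interaction, baseline BMI value, age stratification, and gender stratification". Protocol 12.5.1 and the protocol synopsis list the same terms. One interaction, treatment by visit, is written out and no other is. Read literally, baseline BMI and the two strata enter as main effects only.

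The inference is at a single time point: "Appropriate contrast will be applied for treatment comparisons at Week 56". The model spans many visits: "All subjects will return at approximately 4-week intervals for study assessments" (SAP 2.2). The schedule in protocol Appendix 1 gives 14 post-baseline visits, Weeks 4 to 56.

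Two other analyses matter here. The ANCOVA in SAP 6.6.3 is a Week 56-only model "with treatment, baseline BMI value as a covariate, and age and gender as stratification factors", so its covariate effects are specific to Week 56. In SAP 6.6.2, continuous secondary endpoints "will be analyzed by a similar MMRM model as for the primary endpoint", with the endpoint's own baseline in place of baseline BMI.

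The documents do not give a covariance structure, the correlation of the covariates with percent change in BMI, or the way those effects develop over time.

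**The concern.** A single slope has to serve Week 4 and Week 56 alike. In a generalised least squares fit, visits with little residual variance carry the most weight for a common slope. Change from baseline starts at zero, and the top dose is reached only in Weeks 15-16, so it is plausible that early changes vary less than late ones and that baseline characteristics have had little time to act. In that case the fitted slope reflects the early visits, and the Week 56 comparison is adjusted with a slope that is too small or even of the wrong sign.

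What is at stake is precision. Randomisation balances the covariates between arms, so a wrong slope does not bias the treatment contrast. It leaves in the residual some variance that data already collected could remove.

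**Working it through.** **1. The plan's own power.** Inputs from SAP 2.3: the mid-dose difference "would be 2 units of BMI which represents more than 2 standard errors below what was observed before"; "a within treatment standard deviation of 2.9"; 50/50/100 subjects with 30% dropout, giving 35/35/70. From SAP 6.1, tests are "Two-sided and use a 5% significance level".

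- Mid-dose vs placebo: SE = 2.9 × √(1/35 + 1/35) = 0.693; power = Φ(2/0.693 − 1.96) = 82.3% (81.2% with the t distribution). Stated: about 80%.
- Top-dose vs placebo, also at 2 units: SE = 2.9 × √(1/35 + 1/70) = 0.600; power = 91.5% (91.0% with t). Stated: at least 90%.

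The stated power is reproduced from the raw within-treatment SD, with no credit for covariate adjustment.

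**2. Algebra for a common slope.** Let b be the vector of true visit-specific slopes, S the residual covariance over visits and X the covariate score. The common slope is

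β = (1′S⁻¹b) / (1′S⁻¹1).

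The Week 56 residual variance is S₅₆ + (b₅₆ − β)² Var(X), against S₅₆ with by-visit slopes. Scale the total Week 56 variance within arms to 1, and let R² be the share that the covariates explain. Then

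- share of the possible adjustment that is kept: k = 1 − (1 − β/b₅₆)²;
- squared-SE ratio, plan against by-visit terms: (1 − R²k) / (1 − R²).

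**3. Results.** S, b and R² are all assumptions. In the last two rows the SD rises linearly over visits.

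| Assumed variance and effect over time | β/b₅₆ | k | R² = 2% | 7% | 12% |
|---|---|---|---|---|---|
| Any variance; effect equal at all visits | 1 | 100% | 1.000 | 1.000 | 1.000 |
| Constant variance; effect linear in time | 0.536 | 78% | 1.004 | 1.016 | 1.029 |
| Random walk; effect linear | 0.071 | 14% | 1.018 | 1.065 | 1.118 |
| SD 4 to 8, adjacent correlation 0.90; effect full from Week 16 | 0.393 | 63% | 1.008 | 1.028 | 1.050 |
| SD 2 to 8, adjacent correlation 0.97; effect full from Week 16 | −0.216 | −48% | 1.030 | 1.111 | 1.202 |

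Example, third row: under a random walk only the Week 4 value informs the level, so β/b₅₆ = 1/14. Then k = 1 − (13/14)² = 0.138, and at 7% the ratio is (1 − 0.07 × 0.138)/0.93 = 1.065. In the last row k = 1 − 1.216² = −0.479, which gives (1 + 0.12 × 0.479)/0.88 = 1.202 at 12%. A negative k means that the common slope does slightly worse than no adjustment at Week 56.

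**4. Simulation check.** Complete data, 35/35/70, 14 visits, 1,000 runs per scenario. For the random walk with a linear effect, the SE ratio was 1.014, 1.039 and 1.131 at a covariate-outcome correlation R of 0.2, 0.3 and 0.5. The algebra at R = 0.3 gives √[(1 − 0.09 × 0.138)/0.91] = 1.042. With a constant effect the ratio was 0.996, so the simpler model was then 0.4% tighter. Type I error of the planned model was 3.7% to 6.1% over all scenarios.

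**5. Which rows fit this trial.** The growth table in protocol Appendix 3 hints at a gradual age effect. Over 13 months, about the trial's length, the 95th-percentile BMI rises from 25.6 to 26.5 in boys (3.5%) and from 26.8 to 27.8 in girls (3.7%), starting at 162.5 months. Starting at 192.5 months it rises from 27.6 to 28.3 (2.5%) and from 28.9 to 29.7 (2.8%). The gap between ages typical of the two strata is about 1 percentage point; if it builds linearly, about 1/14 of it is present at Week 4. This is a reference curve. It supports the time shape, not the size of the effect in treated subjects.

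**6. In terms of power.** Suppose the plan as written achieves the step 1 power, and by-visit terms remove a squared-SE excess v. Power becomes Φ(2√v/SE − 1.96). For v = 1.065, 1.11 and 1.20, mid-dose power goes from 82.3% to about 84.6%, 86.0% and 88.5%. For v = 1.11 and 1.20, top-dose power goes from 91.5% to about 93.9% and 95.4%. These are illustrations: the planning inputs are in BMI units, while the endpoint is percent change.

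**The case against.** The strongest reply is that the size rests entirely on inputs the documents do not give. With constant variance the planned model keeps 78% or more of the adjustment, and with constant effects all of it. If R is 0.2 or less, the SE penalty is at most about 3%. This stands, and it is why the point is conditional.

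Second, nothing the plan promises is broken: there is no bias, Type I error holds, and the stated power is met without adjustment. This also stands. The point concerns efficiency.

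Third, the calculations use complete data, whereas SAP 6.6.1 first imputes multiply, from retrieved dropouts or by the washout method. Dropout and between-imputation variance are not modelled, so the figures are indicative.

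Fourth, a Week 56-specific adjusted analysis is already planned. It is, but only as a sensitivity analysis. A reader might infer that primary and sensitivity results therefore cannot be compared. That goes too far: the SAP calls the ANCOVA model only similar and says that it drops the repeated measures, and under randomisation both models target the same Week 56 difference.

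**Conclusion.** The omission is real and worth correcting, as a cheap gain in precision. Under the assumed inputs the planned model's squared standard error at Week 56 is about 0% to 20% larger than with by-visit terms when the covariates explain 2% to 12% of the variance, and about 0% to 11% larger at 7%. The upper end needs variance that grows over follow-up together with effects that build up; the lower end is reached when the effects are constant over visits.

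A reader might infer that the model makes almost no adjustment at Week 56 and that its confidence intervals are certainly too wide. The documents do not support that, because they give neither the covariance, nor the explained variance, nor the time course.

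A reader might also extend the point to every secondary MMRM. That is too broad. The OGTT, the only scheduled source of insulin, is done at baseline and end of study (protocol 10.10), so fasting insulin and the Matsuda index have one scheduled post-baseline assessment. Lipids have two, at Weeks 28 and 56 (protocol Appendix 1). The argument reaches waist circumference and blood pressure, which are measured at every visit.

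**What to change.** Add baseline BMI-by-visit, age-by-visit and gender-by-visit interactions to the primary MMRM in SAP 6.6.1; at minimum, add baseline BMI-by-visit. Add the same terms, with the endpoint's own baseline, to the MMRMs for waist circumference and blood pressure in SAP 6.6.2. Leave the contrast, imputation and testing order as they are.

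Protocol 12.5.1 and the synopsis carry the same term list, and protocol 12.1 calls for an amendment when the primary analysis changes in a major way. Align the protocol wording with the SAP before the database is finalised, so that the two do not diverge.

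The cost is up to 3 × 13 = 39 more fixed-effect parameters in a model with up to 14 × 200 = 2,800 records (repeated measures on 200 subjects), plus the wording changes. No new data are needed. If the covariate effects are in fact constant over visits, the standard error is about 0.4% larger.

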### 6.6.2 Secondary Efficacy Analysis

If both the mid- and top-dose are shown to be statistically significantly better than placebo for the primary endpoint using the Fisher's LSD procedure, then the secondary endpoints will be tested in a stepwise way to preserve the familywise type 1 errors.

Starting from top-dose of VI-0521 treatment, hypothesis tests for secondary efficacy endpoints will be based on null hypotheses that assume no *a priori* differences between placebo and top-dose treatment.

A closed or sequential testing procedure will be used for testing the key secondary efficacy variables. With this hierarchical procedure, the key secondary efficacy variables will only be tested if the primary efficacy analysis is statistically significant.

Analyses will be carried out for the key secondary variables.

Within the key secondary variables, the statistical significance level will be adjusted using the Hochberg method, controlling the familywise error rate at 5%. Correlation

analysis will be implemented among the key secondary variables to ensure the conditions required for Hochberg procedure are satisfied. All endpoints have to be statistically significant in favor of top-dose VI-0521 treatment compared to placebo, after the Hochberg adjustment, in order for the next set in the hierarchy to be tested. The testing is only stopped when all of the alpha is 'exhausted'. The sequential testing will stop at the first endpoint set where top-dose VI-0521 treatment does not demonstrate statistical superiority over placebo.

The above process will be repeated on mid-dose of VI-0521 treatment.

Percent of subjects achieving a reduction  $\geq 5\%$  from baseline in BMI at Week 56 will be analyzed using a logistic regression, with treatment, age and gender stratification as the main effect and baseline BMI value as a covariate at the 0.05 significance level. The adjusted odds ratios between the top-dose and placebo, between the mid-dose and placebo, and between the top-dose and mid-dose will be calculated together with their 95% confidence intervals. The p-values for the comparisons will also be generated.

The percent of subjects achieving a reduction  $\geq 10\%$  and  $\geq 15\%$  from baseline in BMI at Week 56 will be analyzed similarly.

Secondary efficacy endpoints that are continuous variables (change from baseline in waist circumference, fasting insulin, whole body insulin sensitivity index (Matsuda), triglycerides, HDL-C, and systolic and diastolic blood pressure) will be analyzed by a similar MMRM model as for the primary endpoint where the baseline BMI value will be replaced by the baseline value of the corresponding endpoint as a covariate.

The above analyses will be conducted for both the ITT and mITT populations.

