12.5.3 Analysis of the Secondary Endpoints

If both the mid- and top-doses are shown to be statistically significantly better than placebo for the primary endpoint using the Fisher's LSD procedure, then the secondary endpoints will be tested in a stepwise way to preserve the familywise type 1 errors. Details of the stepwise testing procedure for secondary efficacy endpoints will be described in a prospective SAP.

Percent of subjects achieving a reduction $\geq 5\%$ from baseline in BMI at Week 56 will be analyzed using a logistic regression, with treatment, age and gender stratification as the main effect and baseline BMI value as a covariate at the 0.05 significance level. The adjusted odds ratios between the top-dose and placebo and between the mid-dose and placebo will be calculated together with their 95% confidence intervals. The p-values for the comparisons will also be generated.

The percent of subjects achieving a reduction $\geq 10\%$ and $\geq 15\%$ from baseline in BMI at Week 56 will be analyzed similarly.

Secondary efficacy endpoints that are continuous variables will be analyzed by a similar MMRM model as for the primary endpoint where the baseline BMI value will be replaced by the baseline value of the corresponding endpoint as a covariate.

The above analyses will be conducted for both the ITT and m-ITT populations.

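### Top-dose vs mid-dose is tested inside the 5% primary family but is not part of the gate to the secondary endpoints, so the two sets of claims together can exceed 5%

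*SAP*

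**What the plan says.** **Primary family (SAP 6.6.1; same scheme in Protocol 12.5.1).** The comparisons are listed as follows: "The pairwise comparisons of interest are top-dose vs. placebo, and mid-dose vs. placebo, and top-dose vs. mid-dose". After a significant overall test, "the above 3 pairwise comparisons will be conducted using Fisher's LSD method at the 0.05 significance levels". The SAP adds: "Due to the fact that only three treatments are compared, the above procedure strongly controls the family-wise type 1 error". Top vs mid comes last in the stated order but is inside the set for which error control is claimed. The primary null in the same section is narrower and sets only the active groups against placebo.

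**Gate (SAP 6.6.2; same in Protocol 12.5.3).** The secondary endpoints open "If both the mid- and top-dose are shown to be statistically significantly better than placebo for the primary endpoint". A second sentence in SAP 6.6.2 says that "the key secondary efficacy variables will only be tested if the primary efficacy analysis is statistically significant", without naming the comparisons. Protocol 12.5.3 gives the purpose: "then the secondary endpoints will be tested in a stepwise way to preserve the familywise type 1 errors".

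**Secondary family (SAP 6.6.2).** Hochberg is applied within the key secondary variables at a familywise 5%, first for top-dose vs placebo. The process is then repeated for mid-dose, with no statement of order or alpha. The SAP also asks for top-vs-mid odds ratios with p-values for the responder endpoints. Protocol 12.5.3 lists only the two dose-vs-placebo odds ratios.

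**The concern.** A serial gate can pass the full alpha to the next family only if every confirmatory member of the first family has been rejected. Here the gate opens on two of the three. When both doses beat placebo and do not differ from each other, the third test still carries its own 5% chance of a false rejection, and the secondary family starts at another 5%. Nothing links the two.

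At stake is whether a reported dose difference on BMI and the reported secondary findings can all be presented as claims from one error-controlled procedure. The dose-vs-placebo tests on BMI are not in question.

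**Working it through.** **Inputs.** SAP 2.3 gives 50/50/100 subjects (placebo/mid/top) and 30% dropout, hence 35/35/70 evaluable; a planning difference of 2.0 BMI units; an adult difference of 2.4; and SD 2.9. SAP 6.1 sets the tests: "Two-sided and use a 5% significance level". Not in the documents, and therefore assumed: correlation 0 to 0.8 between BMI and a secondary endpoint, and 0.5 or 0.8 among secondary endpoints.

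**1. The plan's own figures.**
- Power, top vs placebo: 2 / (2.9 × √(1/35 + 1/70)) = 3.33; Φ(3.33 − 1.96) = 91.5%, against at least 90% stated.
- Power, mid vs placebo: 2 / (2.9 × √(2/35)) = 2.885; Φ(2.885 − 1.96) = 82.2% (81.2% by t-test), against about 80% stated.
- Error of the three-comparison LSD: if all means are equal, the overall test caps it at 5%. If exactly one pair is equal, only one true null remains, tested at 5%. Simulation (1,000,000 trials) gives 5.01% under the complete null and 5.00% for top vs mid when both doses work equally. The strong-control statement is correct for the three primary comparisons taken alone.

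**2. Adding the top-dose secondary family, gate always open.** With top = mid on BMI and true secondary nulls, each side spends 5%. Under independence: 1 − 0.95 × 0.95 = 9.75%. The sum bound is 5% + 5% = 10%.

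**3. At the documents' effects.** Simulated probability of a false top-vs-mid rejection or a false top-dose secondary rejection (one null secondary endpoint, top = mid):

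| Effect of both doses vs placebo | Gate opens | Correlation 0 | 0.3 | 0.5 | 0.8 |
|---|---|---|---|---|---|
| 2.0 units | 78% | 8.7% | 8.5% | 8.3% | 7.6% |
| 2.4 units | 92% | 9.4% | 9.2% | 9.0% | 8.3% |
| Gate always open | 100% | 9.7% | 9.7% | 9.7% | 9.6% |

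With three correlated secondary endpoints under Hochberg and the gate open, the figure is 8.7-9.2%.

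**4. Is the missing condition the cause?** If the secondaries open only after all three primary comparisons are rejected, the same simulations give 4.9-5.0%. A false secondary claim would then need a false top-vs-mid rejection first.

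**5. The mid-dose repeat.** If it runs in parallel at its own 5% (one endpoint, gate open), the two secondary families alone reach 8.8%, and 12.6-13.4% with top vs mid added. If mid-dose is tested only after full top-dose success, the figures in steps 2 and 3 stand. The SAP does not say which.

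**6. What top vs mid can deliver.** SE = 2.9 × √(1/70 + 1/35) = 0.600. For an assumed true difference of 0.5 units, 0.5/0.600 = 0.83 and power is 13%. For 1.0 unit, 1.0/0.600 = 1.67 and power is 38%.

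**The case against.** The best defence is that top vs mid is not a claim. The stated primary null covers only doses against placebo. Top vs mid is absent from the objectives, the power statement and the gate, and it is ordered last. On that reading the gate requires exactly the comparisons that make up the primary null, and nothing leaks. This stands as a possible reading, and it is why the point is conditional. It does not settle the matter, because SAP 6.6.1 puts top vs mid among the three tests at 0.05 and claims strong control over them. If it is only supportive, the SAP should say so.

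Three stronger readings are tempting but not supported:

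- A reader might infer that equal doses are the likely situation. SAP 2.3 assumes a larger effect for top-dose, and Protocol 4.0 reports adult weight loss above 10% for top-dose and above 8% for mid-dose. If top truly exceeds mid, rejecting that null is correct and this route adds no error. Equality matters because strong control must hold under every configuration.
- A reader might infer that the SAP promises one 5% across both families and breaks it. It states 5% for the primary comparisons and 5% within the key secondary variables, and nothing for the two together. Joint control is a reasonable reading of the stepwise gate's stated purpose, but it is an inference.
- A reader might take 9-10% as the trial's total error. It is a ceiling for an open gate, lower at the planning effects, and it leaves out the mid-dose repeat.

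**Conclusion.** The point holds in conditional form. If top vs mid is confirmatory, the procedure does not keep familywise error at 5% over the primary and secondary claims together. The worst-case figure is 7.6-8.7% at 2.0 units and 8.3-9.4% at 2.4 units, with a maximum of about 9.75%. This rests on top = mid on BMI, both doses better than placebo, true top-dose secondary nulls, 35/35/70 evaluable subjects, SD 2.9 and the assumed correlations. The mid-dose repeat is not counted.

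Severity is should-fix. The LSD claim for the three primary comparisons is sound, both dose-vs-placebo conclusions are unaffected, and the gap closes with a change of wording.

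**What to change.** In SAP 6.6.1 and 6.6.2 and Protocol 12.5.1 and 12.5.3, choose one:

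- state that top vs mid is not part of the confirmatory family, and report it as an estimate with a 95% CI; or
- keep it as a test, but place it last, after the secondary hierarchy.

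Label the top-vs-mid odds-ratio p-values in SAP 6.6.2 as descriptive. They lie outside the placebo-based hierarchy and play no part in the figures above, but their status should be plain. Align the second wording of the gate in SAP 6.6.2 with the first by naming the two comparisons.

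Requiring all three comparisons before the secondaries, or splitting alpha, would also restore control. The first would make the secondary endpoints depend on a comparison with 13-38% power at 0.5-1.0 units, so it is the less attractive route.

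Separately, state the order and alpha of the mid-dose repeat. The change above removes only the top-vs-mid excess.

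The cost is wording, plus the loss of an early confirmatory claim for a low-powered comparison. Protocol 12.1 requires an amendment for major modifications of the primary analysis, and has the SAP signed before the database is final. The change should be made before then, since demoting or moving a comparison afterwards would look data-driven.
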